1 ABREVIATIONS

ADL	Activities of Daily Living
AE	Adverse event
GDS	GeriatricDepresionScale
FC	Fried's Criteria
EC	Ethics Committee
eCRF	Case Report Form
GCP	Good Clinical Practice
EQ-5D	EuroQolfive-dimensional (EQ-5D)
CRO	Contract Research Organization
IADL	Instrumental Activities of Daily Living
INE	Instituto Nacional de Estadística (Spain)
ICF	InformedConsentForm
MMSE	Minimental State Examination
SPPB	Short Physical Performance Battery
PASE	Physical Activity Scale for the Elderly
CAM	Confusion Assessment Method
ICER	Incremental cost-effectiveness ratio
PI	Principal Investigator
HUG-GRT	Hospital Universitario de Getafe-Servicio de Geriatría

2 INTRODUCTION

2.1 BACKGROUND INFORMATION:

Disability is the main consequence of the concurrence of three conditions in old people: the ageing process, lifestyle processes and health-related conditions.

As it has been the case with other relevant organizations and bodies, in its 2012 Ageing report, the European Commission and the Economic Policy Committee stated that coping with the challenge posed by an ageing population and a trend toward increases in age-related spending will require determined policy action in Europe, particularly in: (a) reforming pension, health care and long-term care systems, and (b) the reduction of disability and dependence through appropriate action with a special focus in fighting against disability (DG ECFIN & AWG, 2012).

Disability is usually preceded by a state characterized by a decreasing capacity to respond to demands, caused by diminishing functional reserve. This condition has been named frailty, a disorder that may precede by several years the development of disability (1) and other clinical outcomes. When the frailty threshold has been surpassed and disability has emerged, recovery from disability is unlikely (2), especially as the age of the patient, the degree of disability or its duration increase (3). In contrast, frailty is reversible, as it has been shown both spontaneously (4, 5) and by interventions based on physical exercise (6).

Moreover, and differently from chronic disease, the predictive capacity of frailty for adverse outcomes increases as the age of the population increases (8) becoming the most common condition leading to death among community-dwelling older persons, followed by organ failure (21.4%), cancer (19.3%) and dementia (13.8%) of dying.

The aim of the present study is to assess the feasibility and effectiveness of programs designed to detect and manage frail older patients in high risk clinical settings, and to avoid functional impairment and other associated adverse outcomes.

2.2 RATIONALE OR JUSTIFICATION

The prevalence of frailty in people older than 65 years is high, ranging from 7 to 16.3 %, and this increases with age (1, 9, 10).

The most accepted approach defines frailty as “an age-associated biological syndrome characterized by a decrease in biological reserve and resistance to stress, due to a decline in several physiological systems, placing the individual in a special risk category when facing minor stressors and associated with poor outcomes (disability, death and hospitalization)” (11-14).

Frailty is an established and credible concept which provides the framework for the relationships between ageing, disease, vulnerability, disability, and dependency (15). with its high prevalence in older people and its potential reversibility, make frailty the perfect target to overcome the challenge of disability in older adults(16).

The challenge for Health Systems is develop strategies to detect this syndrome and the prevention the functional decline and disability. As a consequence, a complementary strategy is needed, supporting clinicians to provide personalized, comprehensive continuity of care (17).

Older frail patients are prone to develop functional impairments, to be institutionalized and to die early. Additionally, they use Health and Social facilities much more frequently than their same-age counterparts, being at high risk for mis-, under- and over management. Some of these specific needs are covered by classical Geriatric facilities available in many European Hospitals. But these facilities only attend to 10-15% of all the frail older patients that are being seen and managed by other parts of the health care systems (14)

It has been largely recommended that programs must not only identify at-risk patients so that they may benefit from specialized management, but they must also target the process of care (Lafont E et al., JNHA 2011) to 1) provide the best-fitted models of care to their needs, and 2) adapt the management of their diseases and conditions (cancer, major surgery, heart disease, etc.) to their special features (18). In this regard, recent publications have stated that this approach should be standard practice, and is supported by a wealth of evidence (19), mainly in frail elderly patients being attended in some specific high risk settings as described in our proposal (20-23).

FRAILCLINIC project includes two consecutive phases: the first one focus on detection and quantification of frailty (observational phase) and the second phase focus on management of frail patients by an integrate model of geriatric care (interventional phase). In the observational phase we have evaluated the prevalence of frailty, the success of a program for detection frail patients in high risk clinical settings, tools commonly used for assessment of frailty and causes of no implementation. In the interventional phase we will analyse the effect of the performance of a geriatrician agreed with the treating physician/surgeon of the patient in these clinical settings comparing with the traditional performance.

3 OBJECTIVES

3.1 PRIMARY OBJECTIVE:

To assess the feasibility and effectiveness of programs designed to detect and manage frail older patients in high risk clinical settings, and to avoid functional impairment and other associated adverse outcomes. These high risk settings will be medical wards (cardiology, oncology or nephrology), major surgery wards and Emergency rooms.

3.2 SECONDARY OBJECTIVES:

- Determine the feasibility of implementing clinical and therapeutic approach to geriatric physician in elderly patients in high risk clinical settings
- Determine disability by evaluating basic and instrumental activities of daily living in frail elderly patients treated in high risk clinical settings.
- Establish functional status in frail elderly people seen in high risk clinical settings.
- Evaluate quality of life through an instrument validated in frail patients seen in high risk clinical settings.
- Establish mortality ratio in frail patients included in high risk clinical settings.
- Obtain the rate of re-hospitalization in frail patients seen in high risk clinical settings.
- Determine the average stay of hospitalization in frail elderly patients treated in high risk clinical settings.
- Obtain the rate readmission to emergency room and hospitalization in frail older patients treated in high risk settings.
- Determine the average stay of hospitalization in frail elderly patients treated in high risk clinical settings.
- Determine the rate of delirium in frail elderly patients in high risk settings.
- Obtain the rate of health-care associated infections in frail older patients seen in high risk settings.
- Determine the rate of polypharmacy in frail older patients seen in high risk settings.
- Establish the secondary institutionalization rate accordingly to decline the functional status in frail elderly patients in high risk settings.

- Determine the need for a caregiver as a result of decline the functional status in frail older people in high risk settings.
- Establish the caregiver burden in hospitalized frail patients on high risk settings.
- Establish the secondary institutionalization rate accordingly to decline the functional status in frail elderly patients in high risk settings.
- Determine the need for a caregiver as a result of decline the functional status in frail older people in high risk settings.
- Establish caregiver burden of frail elderly patients seen in high risk settings.
- To evaluate the cost-effectiveness of the intervention compared with usual care from the perspective of society and the health system.
- To evaluate the cost-utility of the intervention compared with usual care.

4 OUTCOMES

4.1 PRIMARY OUTCOMES:

1. **Disability:** It was measured by the Barthel Index for basic Activities of Daily Living and the Lawton index for instrumental activities of daily living.
2. **Functional status and performance-based measures:** Functional status and performance-based measures: Is measured by Short Physical Performance Battery (SPPB), Physical Activity Scale for the Elderly (PASE SCALE).
3. **Quality of Life:** Quality of life was assessed by self-reported questionnaire EuroQL 5D 5L. It will be measured during admission to hospital and follow-up.
4. **Geriatrician Intervention:** The impact of their intervention is measured by quantifying in a register any additional tests requested and medical advice by other specialists.

4.2 SECONDARY OUTCOMES:

Prevalence of Delirium: The delirium cases are detected by Confusion Assessment Method (CAM) scale.

Cognitive Impairment: Will be measured by the Mini Mental State Examination (MMSE) in the initial assessment.

Depression: will be assessed using the Geriatric Depression Scale in the baseline assessment.

Health-care associated infections: Acquired during hospitalization start.

Geriatric Syndromes: The geriatric evaluation including the following aspects: clinical, functional, mental and social.

Comorbidity: Will measured at initial assessment thorough Charlson index

Nutritional Status: Will measured at initial assessment thorough the Mini Nutritional Assessment and body Mass index.

Polypharmacy: Defined as five or more prescription drugs.

Mortality rate: Number of deaths during follow-up. It is calculated using official report of the National Statistics Institute (INE).

Average stay hospitalization: Average length of stay of stay all discharges. We will obtain from Hospital Admissions service.

Hospitalization Rate in Emergency room: Number of hospital admissions over the total of patients admitted in the hospital.

Readmission rates: Number of readmissions during of follow-up period. I will get the data in Hospital Admissions Service.

Institutionalization: Number of patients referred to nursing home after discharge or at any time during follow-up. This information is obtained directly from patients or their relatives.

Requirement of caregiver: Number of patients who require a caregiver after hospital discharge.

Caregiver burden: Will be used Zarit Scale for assessing caregiver burden

Cost-effectiveness: The incremental cost-effectiveness ratio (ICER) was assessed by measuring the difference in health outcomes per unit cost.

Cost-utility: is measured using the QALY (unit of measurement of preferences of individuals with regard to the quality of life that has occurred through a health intervention, combined with the years earned for a given health state).

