9 ASSESSMENTS DURING THE STUDY

9.1 BASELINE EVALUATION (visit 0= FIRST VISIT)

After the inclusion of a participant in the study, a comprehensive geriatric assessment will be done with the following parts:

Demographics and epidemiology: Date of birth, age, sex, race, caregiver, marital status, number of persons in the house, and, number of hospitalization in the last year, follow up by others specialist, level of education.

- Medical history

Personal Medical and Surgery History should be recorded in the electronic Case Report Form (eCRF).

- Medications:

In the CRF we register all the regularly medication use (previous hospitalization)

- Functional status

Evaluate functional status with the following scales: Barthel Index, Lawton Index, measures based in performance (SPPB-Short Physical Performance Battery) and PASE Scale, Annex 2.

- Cognitive and depression:

Evaluate the results with MMSE and Geriatric Depression Scale GDS, and delirium risk with CAM scale. See Index 2.

- Physical examination:

Vital signs and physical examination as usual by the clinical investigator.

- Geriatric Syndromes Assessment:

Immobility: Falls and imbalance.

Incontinence: urinary and fecal.

Sensory deprivation

Iatrogenic: Record the numbers of falls during the hospitalization and adverse effects

Pain: assess pain using the VAS Scale. Nutritional Status:

Performed screening for nutritional status using the scale MNA (Mini Nutritional Assessment), Index 2.

- Comorbidities:

Comorbidities will be quantified by Charlson Index, Index 2.

Quality of Life :

The evaluation for the quality of life using the EuroQol five-dimensional (EQ-5D), Index 2.

Caregiver :

- Assessment for the burden of the caregiver; Will be evaluated with The Modified Caregiver Strain Scale. Index 2.

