9.2 EVALUATION AT DISCHARGE FROM THE SPECIFIC CLINICAL SETTING

The following aspects will be assessed:

- Mortality
- Frailty assessment with L. P. Fried's scale and/or FRAIL scale. Functionality assessment with Barthel Index. Indicate the number of hospital stay in days .
- Describe if the patient change the Ward location/ medical /surgical in the hospital (UCI, Coronary unitetc) o)during the evolution in the hospital
- Quantification the number of test (Blood test, urine test, X- Ray, ecography, CT, etc and more specialized like: PET TAC, echocardiography, polisomnography, etc.)
- Quantification the number of consult with other specialist, social worker, palliative care. Etc.
- Usual treatment (Register all the medication at discharge
- Evaluate if the patient develop geriatric síndrome (page 22).
- Destination at dischargeia. (Nursing home, follow up by home care team, I HUG- GRT, day hospital, rehabilitation at home , specialist consultation, etc.)
- Evaluate the perception of the quality of life with the scale EuroQol five-dimensional (EQ-5D).
- Burden of the caregiver with the Economics questionnaire s.
- Economics evaluation Index 3

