9.3 EVALUATION AT 3 MONTHS OF DISCHARGE

Re-evaluate the following aspects by phone :

- Mortality
- Functionality data (Barthel index , Lawton index , PASE Scale).
- Usual medication.
- Residency at the moment.
- Frailty with the FRAIL scale..
- Data of quality of life with the scale EuroQolfive-dimensional (EQ-5D)
- Number of hospitalization and ER, indicate the cause (diagnosis)
- Caregiver burden with the economic questionaries .
- Economics evaluation, Index 3

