9.4 EVALUATION AT 12 MONTHS OF DISCHARGE

Re-evaluate the following aspects by phone

- Mortality
- Functionality data (Barthel index, Lawton index , PASE Scale).
- Usual medication.
- Residency at the moment.
- Frailty with the FRAIL scale. Datos de fragilidad con la escala FRAIL.
- Data of quality of life with the scale EuroQolfive-dimensional (EQ-5D)
- Number of hospitalization and ER, indicate the cause (diagnosis)
- Burden of the caregiver with the economics questionnaires.
- Economics evaluation., Index 3

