9.5 END OF THE STUDY EVALUATION

- The study will finish at 12 months after patient's discharge with a lastphone call .
- We should make an effort to write all the data during the study, at follow up and the final evaluation..

A follow-up and investigator's tasks schedule was performed during the study. See table 2.

Table 2 Schedule of the investigation

Intervention phase	Eligibility&recruitment	Initial Visit	Discharge	3 month Follow-up	12 month Follow-up
Informed consent	X				
Eligibility CI and CE	X	X			
Medical history		X			
Usual treatment		X	X	X	X
Comprehensive Geriatric Assessment		X			
Cognitive and depression (MMSE,GDS,CAM)		X			
Comorbidities - Charlson I.		X			
Functional Status (Barthel I, Lawton I, PASE, SPBB)		X SPBB	X Barthel	X	X
Sociodemographic data		X			
Physical Exam		X			
Nutritional Status (MNA)		X			
Permanent residence		X	X	X	X
Mean hospital stay			X		
Death			X	X	X
Frailty (Fried)		X	X		
Frailty(FRAIL)		X	X	X	X
EuroQolfive-dimensional (EQ-5D)		X	X	X	X
Caregiver burden		X	X	X	X
Relocation to other hospital services			X		
Adverse events (iatrogenic, falls, geriatric syndromes, etc.)		X	X		
Economics evaluation			X	X	X
Checklist of complementary test during the hospitalization			X		
Consultation to other specialist during hospitalization			X		

Coordination of care in different levels of care		X		
Readmission			X	X
Visits to the emergency room			X	X
Nosocomial infections		X		

* In case of surgical patients, who after 3 weeks since the first visit have passed and surgery hasn't been performed, evaluate the possibility of re-assessing inclusion criteria.

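### Primary outcome 2 names SPPB as its only performance test, but the visit schedule does not assure a post-baseline SPPB in both arms

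*Combined protocol and SAP*

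**What the plan says.** Section 4.1 lists four primary outcomes. The second, covering functional status and performance-based measures, "Is measured by Short Physical Performance Battery (SPPB), Physical Activity Scale for the Elderly (PASE SCALE").

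The visit sections then name the functional instruments as follows.

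- Baseline (9.1): Barthel, Lawton, "measures based in performance (SPPB-Short Physical Performance Battery) and PASE Scale". These stand among the parts of the Comprehensive Geriatric Assessment (CGA) that the section describes.
- Discharge (9.2): "Functionality assessment with Barthel Index", with no other functional scale.
- 3 months (9.3): "Re-evaluate the following aspects by phone", with "Functionality data (Barthel index , Lawton index , PASE Scale").
- 12 months (9.4): also by telephone, with "Functionality data (Barthel index, Lawton index , PASE Scale"). Section 9.5 confirms that the study ends 12 months after "discharge with a lastphone call".

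Table 2 has one row for all four instruments, "Functional Status (Barthel I, Lawton I, PASE, SPBB"). The initial-visit cell is marked for SPPB (spelled SPBB), the discharge cell is marked for Barthel, and the 3- and 12-month cells hold an X with no instrument named. The CGA has a separate row, marked at the initial visit only.

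Section 8.1 gives control patients a CGA at admission and again at discharge. Section 8.2 has the geriatric team carry out a CGA in the intervention arm but states no time for it.

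**The concern.** A randomised comparison on an instrument needs a value after randomisation in both arms. SPPB is the only part of primary outcome 2 that observes performance. If it is not repeated, or is repeated in one arm only, neither a difference at follow-up nor a difference in change from baseline can be estimated for it, whatever the number of patients. The trial would then carry a primary outcome whose name promises a performance-based result that the schedule does not deliver. The gap could not be closed later under the present schedule, because every contact after discharge is by telephone.

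**Working it through.** No sample-size or power figure bears on this point, so the check sets the passages side by side.

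**Step 1. Instruments by visit, from sections 9.1 to 9.4.**

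| Instrument | Baseline | Discharge | 3 months | 12 months | Post-baseline |
|---|---|---|---|---|---|
| Barthel | yes | yes | yes | yes | 3 of 3 |
| Lawton | yes | no | yes | yes | 2 of 3 |
| PASE | yes | no | yes | yes | 2 of 3 |
| SPPB | yes | no | no | no | 0 of 3 |

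**Step 2. Can the unlabelled marks in Table 2 be SPPB?** Read alone, an X at 3 and 12 months in a row that names SPPB could include it. The form in Appendix 2 requires timed balance stands, a timed 4-metre walk and timed chair rises. Sections 9.3 and 9.4 make those contacts by telephone and name the instruments without SPPB. The marks therefore cannot mean SPPB as the visits are planned.

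**Step 3. How far can the labelled cells be trusted?** They are not exhaustive: the initial-visit cell names SPPB alone, although section 9.1 also requires Barthel, Lawton and PASE there. The Barthel label at discharge would be weak evidence by itself, but it agrees with section 9.2.

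**Step 4. The contrary route.** Section 9.1 makes SPPB part of the CGA. Section 8.1 repeats the CGA in controls at discharge. Joined, these imply a discharge SPPB in the control arm. Section 8.2 neither requires nor excludes a discharge CGA in the intervention arm, section 9.2 lists no SPPB and does not distinguish the arms, and Table 2 marks no CGA at discharge.

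**Step 5. What each reading gives.**

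| Reading | Control arm, post-baseline SPPB | Intervention arm, post-baseline SPPB | Between-arm comparison |
|---|---|---|---|
| Section 9 and Table 2 | none | none | not possible |
| 8.1 joined with 9.1 | discharge | not stated | not assured |

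With 1:1 allocation of the 1860 participants in section 7.3, the second reading assures a repeat SPPB in 1860 / 2 = 930, all of them controls.

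**The case against.** The strongest reply is the route through sections 8.1 and 9.1. A reader might infer from section 9 that SPPB is taken at baseline only and that no participant is due a second one. The documents do not support that as a flat statement, since section 8.1 implies a discharge SPPB in controls. Nor do they show that control-only testing was intended, because section 8.2 leaves the time open. What remains is a conflict, and no reading of it assures SPPB in both arms.

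Three other replies carry some weight.

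- Fried's criteria are listed at discharge and include a timed 15-foot walk and grip strength, so some performance data may exist. They are a frailty measure outside primary outcome 2, and section 9.2 lets the FRAIL questions stand in for them.
- Section 7.4 plans to compare how well the scales predict, using logistic models, and a baseline SPPB could serve there. The same section also plans to estimate intervention effects, which a baseline value cannot supply.
- The reach is narrow. A reader might infer that primary outcome 2 as a whole is lost, or that the cost-effectiveness analysis in section 10 fails. Neither follows. PASE is due at baseline, 3 and 12 months, and section 10 speaks of functional status without naming SPPB, so Barthel and PASE can supply change from baseline.

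Section 7.2 puts the later follow-up at month 6 where section 9.4 has month 12. That is a separate inconsistency; section 7.2 does not name SPPB.

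**Conclusion.** The point holds as an internal inconsistency between the outcome list and the visit schedule. As written, SPPB is either not repeated at all or assured at discharge in controls only, and neither reading assures a valid between-arm comparison. It concerns one of two instruments in one of four primary outcomes. PASE still supports the rest of outcome 2, and primary outcomes 1, 3 and 4 and the sample size, which rests on disability, are unaffected. It should be fixed, but it does not undermine the trial as a whole.

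The conclusion rests on two things: that the 3- and 12-month contacts are made by telephone as stated, and that SPPB is done as the appended form describes. It needs no assumption about effect size, variance or power.

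**What to change.** Recommended, by text change only:

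- In section 4.1, make SPPB a baseline covariate, rest primary outcome 2 on PASE at 3 and 12 months, and take performance-based measures out of its name.
- In Table 2, label every functional-status cell with the instruments due at that visit.
- Reconcile sections 8.1, 8.2 and 9.2 with Table 2 so that study assessments at discharge are the same in both arms.

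This takes a protocol amendment and adds no patient contact. The price is that the performance-based claim is given up.

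Optional alternative, if the sponsor wants to keep that claim: schedule SPPB at discharge, identically in both arms, in section 9.2 and Table 2. State whether this means discharge from the clinical setting (9.2) or from hospital (7.2), since the two may differ, for example for emergency-room patients. The cost is one extra physical test per participant, and the effect on SPPB would be known only at discharge. The reconciliation of sections 8.1, 8.2 and 9.2 with Table 2 and the labelling of Table 2 are needed under this option too.

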7.4 STATISTICAL ANALYSIS

Firstly, subject's basal characteristics at recruitment will be analyzed. Descriptive statistics of epidemiological and clinical data will be calculated (described in section 9). This analysis will be done in a conjoint manner, according to treatment and clinical setting (emergency room, general surgery, oncology, cardiology, and nephrology).

To verify the differences between the arms of the study a Mann-Whitney test will be made. Based on the inclusion criteria, it is expected that the differences will be produced by the intervention, and not because of differences between groups.

[figure not shown]
To evaluate the intervention in each clinical setting, the effect of the intervention and its statistical significance will be determined.

These effects shall be broken down into two classes depending on the event. First the prevalence rate, and in case the event's duration could be assessed, evaluate if this duration has changed..

For each outcome described in section 4, comparisons between predictive values of the logistic models for each scale will be made in order to determine which scale is optimal in a global manner, according to clinical setting.

In case the date of death and hospitalization can be obtained, survival models will be done.

Diagram 1. Flowchart of randomized clinical trial

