Detach the next page along the lengthwise perforation, and then tear it in half along the horizontal perforation. Use the upper half of the page (blank) for the Comprehension, Writing, and Drawing items that follow. Use the lower half of the page as a stimulus form for the Reading ("CLOSE YOUR EYES") and Drawing (intersecting pentagons) items.

COMPREHENSION

Listen carefully because I am going to ask you to do something.

Take this paper in your right hand [pause], fold it in half [pause], and put it on the floor (or table).

TAKE IN RIGHT HAND _____ 0 1
FOLD IN HALF _____ 0 1
PUT ON FLOOR (or TABLE) _____ 0 1

READING

Please read this and do what it says. [Show examinee the words on the stimulus form.]

CLOSE YOUR EYES _____ 0 1

WRITING

Please write a sentence. [If examinee does not respond, say: Write about the weather.]

0 1

Place the blank piece of paper (unfolded) in front of the examinee and provide a pen or pencil. Score 1 point if the sentence is comprehensible and contains a subject and a verb. Ignore errors in grammar or spelling.

DRAWING

Please copy this design. [Display the intersecting pentagons on the stimulus form.]

0 1

[figure not shown]
Score 1 point if the drawing consists of two 5-sided figures that intersect to form a 4-sided figure.

Assessment of level of consciousness.

Total Score =
(Sum all item scores.) _____
(30 points max.)

Alert/ Responsive	Drowsy	Stuporous	Comatose/ Unresponsive

CLOSE YOUR EYES

ANEXO 3

Patient's information obtained from his/her clinical record

(Baseline)

1. **Patient's ID:** _____
2. (Register the generic names and total daily dose of drugs that the patient has taken during the last month)

		
		

3. 3. Hospitalization

What was the main cause of hospitalization?

	Diagnosis related Code Group (GRD)	GRD description	Mean stay (days)
			

Questionnaire for the subject(baseline)

1. **Identification number** _____

2. **Level of studies completed**

- Can read and write
- Primary
- Secondary
- University
- None

3. **Is the place where you live of your property?**

- Yes
- No

4. **Number of household members where the subject lives:** _____

people

5. **Carer**

a. **Do you need a carer to assist you with your daily activities?** (for basic hygiene, to help you to move, administration of drugs, performing treatments, etc. Monitoring and supervision tasks are also included)

- Yes
- No ⇒ Skip to question #6

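### Polypharmacy is analysed only as five or more drugs although medication is recorded at four time points; a baseline-adjusted drug count should be added (minor, one secondary outcome)

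*Combined protocol and SAP*

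**What the plan says.** Section 3.2 sets the objective as a rate: "Determine the rate of polypharmacy in frail older patients seen in high risk settings". Section 4.2 gives the only definition, "Polypharmacy: Defined as five or more prescription drugs", with no time point.

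Section 7.4 compares the arms within settings: "To evaluate the intervention in each clinical setting, the effect of the intervention and its statistical significance will be determined". It divides effects by type of event: "First the prevalence rate, and in case the event's duration could be assessed, evaluate if this duration has changed". It then turns to logistic models: "For each outcome described in section 4, comparisons between predictive values of the logistic models for each scale will be made". It names no drug count, change in count or adjustment for the baseline number of drugs.

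Medication itself is collected in more detail. Section 9.1 says "In the CRF we register all the regularly medication use (previous hospitalization", and the baseline form in Annex 3 asks staff to "Register the generic names and total daily dose of drugs that the patient has taken during the last month". Section 9.2 says "Usual treatment (Register all the medication at discharge". Sections 9.3 and 9.4 and Table 2 collect medication again at 3 and 12 months, by phone.

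**The concern.** A patient whose list falls from 11 drugs to 7 scores as unchanged, because both numbers are on the same side of the cut. Only a crossing of the line between four and five registers. If the intervention changes how much is prescribed, a per-setting result of no effect could reflect where the cut lies rather than the care given. The data for a finer measure, including each patient's starting number, are largely in the plan already.

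**Working it through.** **The plan's own figure.** The documents give no rate, effect or power for polypharmacy, so the only figure to reproduce is the sample size, which rests on disability at 40% (section 7.3). The smallest n with n × 0.4 − 1.96 × √(n × 0.4 × 0.6) ≥ 40 is 128. Then 128 × 1.2 = 153.6, or 154, which is close to the stated 155 per arm per setting. After 20% drop-out, 155 × 0.8 = 124 are evaluable per arm. Over the five settings listed in section 7.3, 5 × 124 = 620 per arm.

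**Information lost by the cut.** For a small shift in a normal variable, the efficiency of a cut relative to the mean is φ(z)² / [p(1 − p)]. Here p is the share at or above the cut, z its normal quantile and φ the normal density.

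| Share at or above five | Calculation | Efficiency |
|---|---|---|
| 50% | 0.3989² / 0.25 | 0.64 |
| 70% | 0.3477² / 0.21 | 0.58 |
| 80% | 0.2800² / 0.16 | 0.49 |
| 90% | 0.1755² / 0.09 | 0.34 |
| 95% | 0.1031² / 0.0475 | 0.22 |

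The loss is about 36% at the most favourable placing (1 − 0.64) and 78% at 95% (1 − 0.22). A ceiling makes the loss larger but is not needed for there to be one.

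**Power in one setting.** These inputs are assumptions, not document figures: control mean 5 to 10 drugs, SD 3 to 3.5, one drug fewer in the intervention arm, correlation 0.6 with the baseline number, two-sided 5%.

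Worked case: mean 6, SD 3.5, 124 per arm, cut at 4.5 on the continuous scale.
- Cut: the shares are 0.666 and 0.557, a difference of 0.109. SE = √[(0.666 × 0.334 + 0.557 × 0.443) / 124] = 0.0615. Power = Φ(0.109 / 0.0615 − 1.96) = Φ(−0.19), about 42%.
- Count: SE = 3.5 × √(2/124) = 0.4445. Power = Φ(1 / 0.4445 − 1.96) = Φ(0.29), about 61%.
- Count adjusted for baseline: SE = 0.4445 × √(1 − 0.36) = 0.3556. Power = Φ(1 / 0.3556 − 1.96) = Φ(0.85), about 80%.

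Simulation with rounded-normal counts over the whole range, 124 per arm, approximate power:

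| Control mean | Control share at or above five | Cut | Count | Baseline-adjusted count |
|---|---|---|---|---|
| 5–6 | 56–69% | 41–57% | 58–75% | 77–90% |
| 8 | 84–88% | 35–42% | 58–75% | 77–91% |
| 10 | 94–97% | 20–22% | 58–75% | 77–91% |

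Adjusting the yes/no outcome for the baseline number in a logistic model raises its power at means 5 to 6 to about 51–68%. That is part of the gap, not all of it.

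**Pooled, 620 per arm.** The cut has about 93–100% power at means 5 to 8 and about 78–80% at mean 10. The count has 99% or more throughout.

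**A different model.** With negative binomial counts, SD 3 to 4 and the same one-drug effect, the cut needs between 1.55 and 5.35 times as many patients as the count for 80% power. At the widest SD of 4 the pooled loss starts somewhat earlier: power for the cut is 84% with 81% of controls at or above five, and 73% with 88%.

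**The case against.** **The rate answers the stated objective.** Section 3.2 asks for a rate, and a proportion supplies one. This stands. It is a reason to add the count, not to replace the rate or reduce it to a description.

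**No ceiling is shown.** A reader might infer that nearly all of these frail patients over 75 take five or more drugs in both arms, so that the outcome can hardly move. The documents give no drug count and no prevalence of polypharmacy. At an assumed mean of 6, only about two thirds of controls reach the cut. Only the highest assumed mean looks like a ceiling.

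**Medication review and fewer drugs are inferred.** Section 8.2 describes a Comprehensive Geriatric Assessment leading to a treatment strategy. It does not name medication review, and nothing in the plan predicts a lower count. Section 2.2 mentions under-management as well as over-management, and correcting the former can add drugs. The one-drug effect is therefore illustrative, and a count measures the amount of prescribing, not its quality.

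**Adjustment and the cut are separate matters.** The gain from baseline adjustment should not be credited wholly to dropping the cut. The like-for-like comparison at means 5 to 6 is 41–57% against 58–75%.

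**Other measures exist.** Section 10 lists a count of inappropriate drugs, but only within the parallel cost-effectiveness analyses and with no instrument. It is a different quantity and does not fill the gap. Section 7.4 also names a Mann-Whitney test between arms, but does not attach it to any drug variable.

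**Completeness at follow-up.** Full lists are explicit at baseline and discharge. At 3 and 12 months the protocol asks only for usual medication by phone, so a complete count there is an inference.

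**Conclusion.** The point holds as a minor one. The plan reduces polypharmacy to a yes/no at five drugs and names no analysis of the number of drugs or of its baseline value. About a third of the information is lost at best under a small normal shift, and half to nearly four fifths if 80–95% of patients exceed the cut.

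The practical cost is in the per-setting comparisons. There the cut has roughly 20–57% power under the stated assumptions, against 58–75% for the count and 77–91% for the count adjusted for baseline. Pooled, the loss is small with SD 3 to 3.5 unless about 90% or more exceed five drugs. All the power figures rest on assumed means, SDs, correlation and effect.

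A reader might conclude that the outcome is bound to miss an effect, or that the rate is the wrong outcome. The documents support neither. One secondary outcome is affected; the primary outcomes and the sample size are not.

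**What to change.** 1. Keep the rate of five or more drugs, so that the objective in section 3.2 is still answered, and state the time points at which it is compared. Adjust its logistic model for the baseline number of drugs.
2. Add to sections 4.2 and 7.4, as an inferential secondary analysis, the number of regular prescription drugs at discharge, 3 and 12 months. Compare arms with a linear or count model adjusted for baseline number, centre and setting. Within one setting, the setting term drops out.
3. State how drugs are counted, and that the two phone visits record a complete list.
4. State that the count describes how much is prescribed, not whether it is appropriate.

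The cost is wording and one more secondary analysis. No new variable is needed, provided that the phone visits do capture full lists.
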